1.1 Study design

This is a 6-cohort, multicenter prospective study in up to 88 participants with relapsing multiple sclerosis (MS). Up to 66 of the participants will begin treatment with ofatumumab or already be on commercial ofatumumab, the remaining 22 participants will remain on interferon or glatiramer acetate.

In this study, participants must intend to receive or have received a full course (2 doses) of a non-live coronavirus 2019 (COVID-19) messenger ribonucleic acid (mRNA) (Pfizer or Moderna) vaccine. Participants also must meet inclusion criteria and not meet exclusion criteria.

The study consists of 2 periods as outlined below.

Screening period

Participants will enter a screening period of up to 7 days to assess eligibility requirements. Participants in Cohorts 1, 2, 4 and 6 without Hepatitis B virus (HBV) and total serum immunoglobulin results within the past 6 months prior to screening will require central labs to be drawn. Participants with HBV and total serum immunoglobulin results within the specified inclusion range the past 6 months prior to screening will not require the labs to be drawn.

Treatment period

Participants will obtain the mRNA vaccine through their HCP (private insurance) or appropriate federal, state or local program. Participants should be instructed to provide documentation of vaccine administration to the Study Doctor at the next scheduled on-site study visit.

Cohort 1: Relapsing MS participants receiving a full course (2 doses) of a non-live COVID-19 mRNA vaccine ≥2 weeks prior to ofatumumab start.

For participants who receive the Pfizer vaccine, the first of three 20 mg subcutaneous (s.c) ofatumumab loading doses will be administered on Day 36 or 2 weeks after receiving a full course (two doses) of a COVID-19 vaccine. The 2nd and 3rd loading doses should be administered on Day 43 and Day 50 or 7 and 14 days respectively after the 1st loading dose. Subsequent dosing includes 20 mg s.c. administered monthly starting at Day 64.

For participants who receive the Moderna vaccine, the first of three 20 mg s.c ofatumumab loading doses will be administered on Day 43 or 2 weeks after receiving a full course (two doses) of a COVID-19 vaccine. The 2nd and 3rd loading doses should be administered on Day 50 and Day 57 or 7 and 14 days respectively after the 1st loading dose. Subsequent dosing includes 20 mg s.c administered monthly starting at Day 71.

Cohort 2: Relapsing MS participants receiving a full course (2 doses) of a non-live COVID-19 mRNA vaccine ≥4 weeks after ofatumumab start.

Will continue taking their prescribed ofatumumab as per their current dosing schedule.

Cohort 3: Relapsing MS participants receiving a full course (2 doses) of a non-live COVID-19 mRNA vaccine ≥4 weeks after start of prescribed interferon or glatiramer acetate.

Will continue administration of their prescribed interferon or glatiramer acetate as per their current dosing schedule.

Cohort 4: Relapsing MS participants having completed a full course (2 doses) of a non-live COVID-19 mRNA vaccine ≥4 weeks after ofatumumab start.

Will continue taking their prescribed ofatumumab as per their current dosing schedule.

Cohort 5: Relapsing MS participants having completed a full course (2 doses) of a non-live COVID-19 mRNA vaccine ≥4 weeks after glatiramer acetate or interferon start.

Will continue taking their prescribed glatiramer acetate or interferon as per their current dosing schedule.

Cohort 6: Relapsing MS participants having completed a full course (2 doses) of a non-live COVID-19 mRNA vaccine ≥4 weeks after ofatumumab start and having received a booster ≥14 days prior to screening.

Will continue taking their prescribed ofatumumab as per their current dosing schedule.

Study completion

According to the protocol, study completion is defined as when the last participant completes the end of study (EOS) visit. Participants who discontinue study treatment or who decide they do not wish to participate in the study further should NOT be considered withdrawn from the study UNLESS they withdraw their consent. Where possible, they should return for the EOS visit.

Study design schematics for Cohorts 1, 2 and 3 are shown in Figures 1, 2, 3 and 4. Study design schematics for Cohorts 4, 5 and 6 are shown in Figures 5 and 6.

Figure 1 Study Design (Cohort 1, Pfizer)

[figure not shown]

Figure 2 Study Design (Cohort 1, Moderna)

[figure not shown]

Figure 3 Study Design (Cohorts 2 and 3, Pfizer)

[figure not shown]

Figure 4 Study Design (Cohorts 2 and 3, Moderna)

[figure not shown]

Figure 5 Study Design (Cohorts 4, 5 and 6, Pfizer)

[figure not shown]
[figure not shown]

Figure 6 Study Design (Cohorts 4, 5 and 6, Moderna)

Primary analysis time point

The primary analysis time point is Visit 4 for Cohorts 1, 2 and 3, and Visit 2 for Cohorts 4, 5 and 6.

Interim analysis

For the purpose of early dissemination of results, an interim analysis (IA) will be performed once Cohorts 2 and 4 in combination have ≥ 10 participants enrolled that have had their serum drawn ≥ 14 days after full course (2 doses) vaccination.

A second IA will be performed once Cohort 6 has ≥ 10 participants.

A third IA will be performed once Cohorts 2 – 5 have full enrollment with blood drawn ≥ 14 days after full course (2 doses) vaccination.

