##### Cohort 1:

For participants who receive the Pfizer vaccine, the first of three 20 mg s.c ofatumumab loading doses will be administered on Day 36 or 2 weeks after receiving a full course (two doses) of a COVID-19 vaccine. The 2nd and 3rd loading doses should be administered on Day 43 and Day 50 or 7 and 14 days respectively after the 1st loading dose. Subsequent dosing includes 20 mg s.c. administered monthly starting at Day 64.

For participants who receive the Moderna vaccine, the first of three 20 mg s.c ofatumumab loading doses will be administered on Day 43 or 2 weeks after receiving a full course (two doses) of a COVID-19 vaccine. The 2nd and 3rd loading doses should be administered on Day 50 and Day 57 or 7 and 14 days respectively after the 1st loading dose. Subsequent dosing includes 20 mg s.c administered monthly starting at Day 71.

**Cohort 2:** Will continue taking their prescribed ofatumumab as per their current dosing schedule.

**Cohort 3:** Will continue administration of their prescribed interferon or glatiramer acetate as per their current dosing schedule.

[figure not shown]
**Cohort 4:** Will continue taking their prescribed ofatumumab as per their current dosing schedule and should adhere to the visit schedule as shown in either [Table 8-5](#) (Pfizer) or [Table 8-6](#) (Moderna).

**Cohort 5:** Will continue taking their prescribed glatiramer acetate or interferon as per their current dosing schedule and should adhere to the visit schedule as shown in either [Table 8-5](#) (Pfizer) or [Table 8-6](#) (Moderna).

[figure not shown]
**Cohort 6:** Will continue taking their prescribed ofatumumab as per their current dosing schedule and should adhere to the visit schedule as shown in either [Table 8-5](#) (Pfizer) or [Table 8-6](#) (Moderna).

[figure not shown]
Study design schematics for Cohorts 1, 2 and 3 are shown in [Figure 3-1](#), [Figure 3-2](#), [Figure 3-3](#), and [Figure 3-4](#). Study design schemas for Cohorts 4, 5, and 6 are shown in [Figure 3-5](#) and [Figure 3-6](#).

[figure not shown]
[figure not shown]
[figure not shown]

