### 5.1 Inclusion criteria

Participants eligible for inclusion in Cohort 1 of this study must meet **all** of the following criteria:

1. Signed informed consent must be obtained prior to participation in the study
2. Age 18-55 years old inclusive at Screening
3. Diagnosis of relapsing MS by 2017 revised McDonald criteria
4. Must be willing to comply with the study schedule
5. Will be receiving an mRNA COVID-19 vaccine (Pfizer or Moderna vaccine) at least two weeks prior to starting ofatumumab
6. Eligible to receive and plan to be started on ofatumumab according to the approved labeling
7. Pre-ofatumumab serology with Hepatitis B testing not indicative of active or latent infection
8. Total serum immunoglobulin IgG  $\geq 400$  mg/dl at Screening

Participants eligible for inclusion in Cohort 2 of this study must meet **all** of the following criteria:

1. Signed informed consent must be obtained prior to participation in the study
2. Age 18-55 years old inclusive at Screening
3. Diagnosis of relapsing MS by 2017 revised McDonald criteria
4. Must be willing to comply with the study schedule
5. Will be receiving an mRNA COVID-19 vaccine (Pfizer or Moderna vaccine)
6. Currently on commercially prescribed ofatumumab for  $\geq 4$  weeks for the treatment of RMS
7. Pre-ofatumumab serology with Hepatitis B testing not indicative of active or latent infection
8. Total serum immunoglobulin IgG  $\geq 400$  mg/dl at Screening

Participants eligible for inclusion in Cohort 3 of this study must meet **all** of the following criteria:

1. Signed informed consent must be obtained prior to participation in the study
2. Age 18-55 years old inclusive at Screening
3. Diagnosis of relapsing MS by 2017 revised McDonald criteria

4. Must be willing to comply with the study schedule
5. Will be receiving an mRNA COVID-19 vaccine (Pfizer or Moderna vaccine)
6. Currently on commercially prescribed interferon or glatiramer acetate for  $\geq 4$  weeks for the treatment of RMS
7. Total serum immunoglobulin IgG  $\geq 400$ mg/dl at Screening

Participants eligible for inclusion in Cohort 4 of this study must meet **all** of the following criteria:

1. Signed informed consent must be obtained prior to participation in the study
2. Age 18-55 years old at Screening
3. Diagnosis of relapsing MS by 2017 revised McDonald criteria
4. Must be willing to comply with the study schedule

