### **6.1.3 Treatment cohorts**

- Cohort 1: RMS participants receiving non-live COVID-19 mRNA vaccine at least two weeks prior to ofatumumab start.
- Cohort 2: RMS participants receiving non-live COVID-19 mRNA vaccine at least 4 weeks after ofatumumab start.
- Cohort 3: RMS participants receiving non-live COVID-19 mRNA vaccine at least 4 weeks after start of prescribed interferon or glatiramer acetate.
- Cohort 4: RMS participants having completed a full course (2 doses) of a non-live COVID-19 mRNA vaccine  $\geq$  4 weeks after ofatumumab start.
- Cohort 5: RMS participants having completed a full course (2 doses) of a non-live COVID-19 mRNA vaccine  $\geq$  4 weeks after glatiramer acetate or interferon start.
- Cohort 6: RMS participants having completed a full course (2 doses) of a non-live COVID-19 mRNA vaccine  $\geq$  4 weeks after ofatumumab start and having received a booster  $\geq$  14 days prior to screening

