2.4.1.1 Visit windows

Visit windows will be used for data that are summarized by visit; they are based on the study evaluation schedule and comprise a set of days around the nominal visit day. When visit windows are used, all visits, including unscheduled visits, will be re-aligned (i.e., they will be mapped into one of the visit windows). In the case of major deviations from the visit schedule, or due to unscheduled visits, several assessments for a participant may fall in a particular visit window (either scheduled or unscheduled). Approaches for handling multiple assessments in a visit window are outlined below.

The following steps are used to determine the cut-offs for visit windows:

- The visit window associated with the previous assessment ends prior to the middle point; the visit window associated with the latter assessment begins after the middle point. In case the middle point is an exact study day, it will belong to the previous assessment.
- The visit window of the first post-vaccination assessment starts the day after the second dose of the COVID-19 vaccine for Cohorts 1 – 5, and the day after the COVID-19 vaccine booster for Cohort 6, unless otherwise specified.

Tables 2 – 10 provide visit windows for applicable parameters.

Table 2**Cohort 1 visit windows for SARS-CoV-2 qualitative antibody / CD19+ B cells / T cell**

Analysis visit	Nominal time point	Scheduled visit day (target study day)	Visit window (study days)
Pfizer vaccine:			
Pre-vaccination	Day 1	1	≤1
14 days post-vaccination	Day 36	36	(vaccine day + 1) to 64
70 days post-vaccination	Day 92	92	65 to 147
180 days post-vaccination	Day 202	202	148 to 247
270 days post-vaccination	Day 292	292	248 to 337
360 days post-vaccination	Day 382	382	≥338
Moderna vaccine:			
Pre-vaccination	Day 1	1	≤1
14 days post-vaccination	Day 43	43	(vaccine day + 1) to 71
70 days post-vaccination	Day 99	99	72 to 154
180 days post-vaccination	Day 209	209	155 to 254
270 days post-vaccination	Day 299	299	255 to 344
360 days post-vaccination	Day 389	389	≥345

Note:

- Pre-vaccination and study day are derived as outlined in [Section 2.1.1](#).
- Vaccine day is the study day of the second dose of the COVID-19 vaccine.
- Assessments performed between the first and second doses of the COVID-19 vaccine are not assigned an analysis visit.

Table 3**Cohort 1 visit windows for serum immunoglobulin (IgG, IgM)**

Analysis visit	Nominal time point	Scheduled visit day (target study day)	Visit window (study days)

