2.5.1 Primary endpoint(s)

The primary endpoint is achieving immune response as defined by a positive SARS-CoV-2 qualitative IgG antibody assay ≥ 14 days after full course (2 doses) vaccination (yes/no).

The primary estimand is described by the following attributes:

- **Population:** Defined through appropriate inclusion/exclusion criteria to reflect the targeted population. Relapsing MS participants subdivided into 6 cohorts. (1) Will receive a full course (2 doses) of a COVID-19 mRNA vaccine ≥ 2 weeks prior to starting ofatumumab 20 mg s.c. treatment; (2) Will receive a full course (2 doses) of a COVID-19 mRNA vaccine after ≥ 4 weeks of commercial ofatumumab 20 mg s.c. treatment (3) Will receive a full course (2 doses) of a COVID-19 mRNA vaccine after ≥ 4 weeks of interferon or glatiramer acetate treatment (4) Completed a full course (2 doses) of a COVID-19 mRNA vaccine after ≥ 4 weeks of commercial ofatumumab 20 mg s.c. treatment but has not yet received a COVID-19 mRNA booster (5) Completed a full course (2 doses) of a COVID-19 mRNA vaccine after ≥ 4 weeks of interferon or glatiramer acetate (may or may not have received a COVID-19 mRNA booster) (6) Completed a full course (2 doses) of a COVID-19 mRNA vaccine after ≥ 4 weeks of commercial ofatumumab 20 mg s.c. treatment and received an additional booster vaccine ≥ 14 days prior to screening
- **Variable:** Achieving immune response as defined by a positive SARS-CoV-2 qualitative IgG antibody assay ≥ 14 days after full course (2 doses) vaccination (yes/no)
- **Treatment of interest:** Non-live COVID-19 mRNA vaccine either ≥ 2 weeks prior to ofatumumab start or ≥ 4 weeks after ofatumumab start or while on interferon or glatiramer acetate
- **Intercurrent event:** Discontinuation of treatment/study, or death
- **Summary measure:** Proportion of participants achieving immune response

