2.5.3 Handling of intercurrent events

Non-response imputation (NRI) approach will be applied to missing post-vaccination antibody assay regardless of intercurrent events.

NRI is a conservative imputation method for dichotomous variables. NRI assumes that a participant is a treatment failure if the participant discontinues the study prematurely. Hence, for missing data the primary endpoint will be imputed as “No”. Refer to [Section 5.1.3.3](#).

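### In Cohort 1 the ±3-day window at Visit 4 permits the first ofatumumab dose and the primary sample 11 to 13 days after vaccine dose 2, below the stated 14-day minimum, and the SAP would count such a sample

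*SAP*

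**What the plan says.** **The minimum.** SAP 1.1 describes Cohort 1 as "Relapsing MS participants receiving a full course (2 doses) of a non-live COVID-19 mRNA vaccine ≥2 weeks prior to ofatumumab start", and the estimand in SAP 1.2.1 and 2.5.1 repeats the condition. Item 5 of the Cohort 1 inclusion criteria (protocol 5.1) reads "Will be receiving an mRNA COVID-19 vaccine (Pfizer or Moderna vaccine) at least two weeks prior to starting ofatumumab". Protocol 6.1.3 has "RMS participants receiving non-live COVID-19 mRNA vaccine at least two weeks prior to ofatumumab start". Neither protocol passage names the second dose; the SAP does, by referring to the two-dose course. The primary endpoint (SAP 2.5.1) is a "positive SARS-CoV-2 qualitative IgG antibody assay ≥ 14 days after full course (2 doses) vaccination (yes/no".

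**The target.** For Pfizer recipients, protocol 3 says the first loading dose "will be administered on Day 36 or 2 weeks after receiving a full course (two doses) of a COVID-19 vaccine". Protocol 6.3.2 places that dose at Visit 4. The scheduling guidance in protocol 8 sets the Visit 4 samples at 14 days after dose 2. SAP 1.1 makes Visit 4 the primary analysis time point for Cohort 1.

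**The tolerance.** Table 8-1 (Cohort 1, Pfizer) gives Visit 4 a window of ±3 days. In Table 8-2 (Cohort 1, Moderna) the second part shows ±3 days and the first part leaves the cell empty. Tables 8-3 and 8-4 (Cohorts 2 and 3) give the same visit +3 days only.

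**The analysis rules.** SAP 2.4.1.1 states: "The visit window of the first post-vaccination assessment starts the day after the second dose of the COVID-19 vaccine" for Cohorts 1 to 5. The Pfizer row of SAP Table 2 for the 14-day visit reads "vaccine day + 1) to 64"; the Moderna row ends at Day 71. SAP 2.5 defines a responder by a positive assay following the two-dose course, with no day count. Under SAP 5.1.3.3, non-response is assumed when no valid assessment exists following both doses; SAP 2.5.3 says that "for missing data the primary endpoint will be imputed as" No.

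**The concern.** The target for Visit 4 sits exactly on the minimum, so any tolerance on the early side breaks the minimum. A participant seen three days early complies with the assessment schedule, yet starts ofatumumab sooner than the cohort definition allows and gives a primary sample that the endpoint definition does not cover. No sentence in either document says that the 14-day minimum overrides the visit window.

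Two things are at stake. The first is the regimen: the interval between vaccination and drug start is what defines Cohort 1, and the schedule lets it fall short. The second is the endpoint: the reported response rate can include samples taken too early for its own definition. Cohort 1 needs the floor for both drug start and blood draw, yet it has the looser window. The cohort groups reported side by side therefore have different earliest permitted sampling times, and the documents give no reason for the difference. The SAP also does not tabulate the defining interval: SAP 2.4.1 summarises times from the MS therapy to the first vaccine dose and to the primary time point, not from vaccine dose 2 to ofatumumab.

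**Working it through.** **Inputs**
- Pfizer, Table 8-1: dose 2 on Day 22, Visit 4 on Day 36, window ±3 days.
- Moderna, Table 8-2: dose 2 on Day 29, Visit 4 on Day 43, window ±3 days (second part of the table only).
- Cohorts 2 and 3, Tables 8-3 and 8-4: same nominal days, window +3 days.
- SAP Table 2: the 14-day visit runs from the day after dose 2 to Day 64 (Pfizer) or Day 71 (Moderna).

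**1. Nominal interval (reproduces the plan).** Interval = Visit 4 day − dose 2 day.
- Pfizer: 36 − 22 = 14 days.
- Moderna: 43 − 29 = 14 days.

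**2. Permitted interval under ±3 days.**
- Pfizer: Days 33 to 39, so 33 − 22 = 11 to 39 − 22 = 17 days.
- Moderna: Days 40 to 46, so 40 − 29 = 11 to 46 − 29 = 17 days.
- Of the seven permitted days (11, 12, 13, 14, 15, 16, 17), three are below 14.

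Visit 4 is scheduled from the actual date of dose 2 (protocol 8), so these intervals do not depend on dose 2 falling on its nominal day.

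**3. What the SAP does with an early sample.**
- Pfizer window: Day 23 to Day 64, which is 1 to 64 − 22 = 42 days after dose 2.
- Moderna window: Day 30 to Day 71, which is 1 to 71 − 29 = 42 days after dose 2.
- A sample at 11, 12 or 13 days lies inside both. It is a valid assessment following both doses, so the trigger in SAP 5.1.3.3 is not met. It also satisfies the responder definition in SAP 2.5 if positive. The three rules together lead to counting it, although SAP 2.5.1 requires at least 14 days.

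**4. Permitted interval under +3 days.**
- Pfizer: Days 36 to 39; Moderna: Days 43 to 46. Both give 14 to 17 days, and 0 of 4 permitted days are below 14.

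**5. Later doses under +3 days.** With a first dose at the latest permitted day, doses 7, 14 and 28 days afterwards fall as follows.
- Pfizer: Days 46, 53 and 67, against targets 43, 50 and 64 ±3.
- Moderna: Days 53, 60 and 74, against targets 50, 57 and 71 ±3.

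All stay inside the windows of Visits 5, 6 and 7.

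**The case against.** The strongest reply is that the text already fixes the timing. Protocol 3, 6.3.2 and 8 all aim at two weeks or 14 days, protocol 8 asks for visits as near the designated day as possible, and an inclusion criterion should outrank a general table tolerance. This has weight, but a visit window exists to state the permitted departure from target, and no sentence ranks the two. It is also true that protocol 2.1 (Cohort 1 population) and 4.1 say two weeks without a lower bound, and protocol 12.4.1 says 14 days. The explicit minimum rests on protocol 5.1 and 6.1.3, the SAP cohort definition and the endpoint.

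A second reply is that an early first dose could surface among the protocol deviations that SAP 2.3.1 summarises by cohort group. It could, but whether a visit inside its window would be recorded as a deviation is uncertain.

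A third is that the analysis-window rule is not peculiar to Cohort 1: SAP Table 5 opens the same way for Cohorts 2 and 3. That is correct. The difference is that their +3-day window keeps schedule-compliant samples at 14 days or later.

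A reader might infer that an early positive sample would be set to non-response, moving the Cohort 1 rate by 1/22 = 4.5 points for one participant, up to 3/22 = 13.6 points for three. The documents do not support that: step 3 shows that the SAP rules point to counting the sample, and no number of early visits is given. A reader might also infer that early ofatumumab lowers the Visit 4 result. Protocol 6.3.2 has treatment given once the visit's assessments are done, so it cannot.

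**Conclusion.** The conflict is real and minor. For Pfizer recipients in Cohort 1 it is clear from Table 8-1; for Moderna recipients it rests on one of the two parts of Table 8-2. The schedule permits the first ofatumumab dose and the primary sample on 3 days out of 7 that fall below the stated minimum, and the SAP would include such a sample in the primary response rate despite its own 14-day requirement.

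The size stops there. The number of participants seen on days 11 to 13 is unknown and may be 0. Neither a shift in the response rate nor an effect on later response can be derived from the documents. The analysis is descriptive with no hypothesis test, and the sample size is unaffected.

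**What to change.** Set the Cohort 1 Visit 4 window in Tables 8-1 and 8-2 to +3 days, as in Tables 8-3 and 8-4. The cost is 4 permitted days at Visit 4 instead of 7, and a written protocol amendment with sponsor and IRB approval, and health authority approval where required (protocol 14.1).

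This may come too late. The documents do not give enrolment status, but the SAP amendment is dated 28-Jun-2023, ahead of database lock, and the first dose falls 382 − 36 = 346 days before the nominal end-of-study visit on the Pfizer schedule. If Cohort 1 dosing is already complete, add to SAP 2.4.1 a Cohort 1 summary of days from vaccine dose 2 to the first ofatumumab dose and to the Visit 4 sample, with values under 14 flagged. Vaccination, dosing and sampling records are already collected, so the cost is one descriptive table.
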